7.3 Completion and Discontinuation

A patient who withdraws from the study prior to meeting all eligibility criteria or prior to having the device installed in their home will be considered a screen failure. All withdrawals past this point will be considered a withdrawal and be counted as a

discontinuation. In the event that a patient has a home installation and has not yet met all eligibility criteria but decides to withdraw from the study due to a device issue (i.e. leaking, alarms, etc.), then the patient will be considered as discontinued and NOT as a screen failure.

A patient is considered to have completed the study when he/she ceases active participation in the study because the patient has, or is presumed to have, completed all study procedures according with the protocol (with or without protocol deviations). Any other cases are classified as discontinuation.

Reasons for completion/discontinuation will be reported on the Completion/Discontinuation electronic case report form (eCRF), including:

- Adverse event
- Change to another dialysis center
- Death
- Disease progression
- Home feed water affected by boil water advisory
- Inadequate dialysis
- Investigator discretion
- Lost to follow-up
- Met an exclusion criteria
- Missed more than 4 consecutive days of therapy
- Consistently missed more than 1 prescribed treatment per week
- Pregnancy
- Protocol violation
- Renal transplant
- Termination of the study
- Voluntary withdrawal
- Water device replacement
- Other

Regardless of the reason, all data available for the patient up to the time of completion/discontinuation should be recorded on the appropriate eCRF.

Every effort will be made to have discontinued patients complete the study completion/termination visit. If the completion/termination visit is done as an additional, unscheduled visit, the assessment results shall be recorded with the completion/termination visit. If a patient terminates participation in the study and does not return for the completion/termination visit, his/her last recorded assessments shall remain recorded with his/her last visit. The reason for discontinuation will be recorded and the data collected up to the time of discontinuation will be used in the analysis and included in the clinical study report.

Patients who discontinue may be allowed to reenroll in the study. These patients will have separate but linked patient IDs (one for each enrollment in the study); this will be captured in the eCRF. These patients will be assigned one unique USUBJID during SDTM creation. Unless otherwise specified, for all patient-related analyses (e.g. demographics and baseline characteristics), these data will be summarized only once in tables, and all data will be listed next to their corresponding USUBJID in listings. For all device-related analyses (e.g. chemical composition testing of dialysis solution, microbiological testing of product water), all data gathered will be summarized and listed.

8. DEMOGRAPHICS AND BASELINE CHARACTERISTICS

Demographics (age, sex, race, ethnicity), baseline characteristics (height, weight, body mass index [BMI]), primary renal diagnosis etiology, whether the patient had a caretaker, and baseline Kt/V_{urea} will be summarized descriptively. A listing for this data will also be generated. For patients who have re-enrolled, demographics and baseline characteristics will be summarized once using the information from their most recent enrollment. If values are different for subsequent enrollments, they will be listed only.

9. MEDICAL HISTORY AND CONCOMITANT MEDICATION

Medical history and non-drug therapies will be coded using the Medical Dictionary for Regulatory Activities (MedDRA) and listed. Concomitant medications will be coded using the WHO Drug Dictionary.

Medical history, concurrent medical conditions, renal medical history, and concomitant medications will be listed. Concurrent medical conditions and concomitant medications will be classified as “Prior” and “Concurrent”, depending on when the start date and end date is with respect to the date of first treatment. All medications that start and end prior to the date of first treatment will be classified as “Prior”, and those that have any amount taken after the date of first treatment will be classified as “Concurrent”. The date of first

treatment will be defined as the first day the patient had ever received treatment from the Point of Care device. If they stopped treatment and re-enrolled, the date of first treatment from the first enrollment will be used to determine Prior or Concomitant medications.

For patients who have re-enrolled, data will be pooled, and all unique medical history, concurrent medical conditions, renal medical history, and concomitant medications will be listed.

10. IN-CENTER TRAINING PERIOD

The following data is collected in regards to the in-center training:

- Whether the patient completed device specific training
- Whether the patient completed comprehension and retention testing
- Date of testing
- Reason if they did not complete testing
- Whether the care partner completed device specific training (if applicable)
- Whether the care partner completed comprehension and retention testing (if applicable)
- Date of care partner's training (if applicable)
- Whether PI concluded patient's PD prescription is stable and can begin treatment at home

All of the above will be listed only. For patients who have re-enrolled, data will be listed for each instance of training.

11. TREATMENT COMPLIANCE AND EXPOSURE

11.1 Treatment Compliance

Compliance will be assessed regularly by the Investigator by reviewing the patient's Sharesource Platform data and eDiary entries. The patient will be instructed to complete the eDiary daily to document treatment activities including, but not limited to, the following:

- Treatment interruptions
 - Confirmation if the patient contacted dialysis center for support with a product or health-related issue
 - Confirmation if the patient was able to sleep during treatment
-
- 

- Treatment outcome (i.e., complete treatment, incomplete treatment) and reasons for incomplete treatment
- Confirmation if the patient altered their treatment parameters
- Investigational product supply requirements

The above eDiary data (with the exception of the investigational product supply requirements) will be summarized using frequencies and percentages for the number of patients experiencing at least one event and the total number of events per total treatments, and it will be summarized continuously using mean, standard deviation, minimum, median, and maximum for the total number of occurrences per patient. These data will also be listed.

For patients who have re-enrolled, the eDiary data will be pooled together.

Interruptions to therapy will be summarized using frequencies and percentages of the following:

- Number of interruptions per patient
- Reason for interruption
- Whether the patient was on standard of care PD therapy

The length of treatment interruption for all interruptions as well as per patient will be summarized for all interruptions using n, mean, median, standard deviation, minimum, and maximum.

The length of treatment interruptions for all interruptions will be calculated as follows:

$$\frac{\sum_{i=1}^t (\text{Treatment restart date} - \text{Date of interruption})}{t},$$

where i is each interruption and t is the total number of interruptions.

The length of total treatment interruptions per patient will be calculated as follows:

$$\frac{\sum_{i=1}^n \sum_{j=1}^m (\text{Treatment restart date} - \text{Date of interruption})}{n},$$

where j is each interruption per patient, m is the total number of interruptions per patient, i is each patient, and n is the total number of patients with an interruption.

11.2 Protocol Deviations

Protocol deviations will be summarized for all patients. Patient counts will be presented for minor protocol deviations, major protocol deviations, and for each category of major protocol deviation.

Protocol deviations will also be listed. The listing will include site ID, patient ID, age, sex, race, weight at baseline (kg), verbatim description of the protocol deviation, date the protocol deviation occurred, the version of the protocol that the deviation occurred under, the assigned classification of protocol deviation, and whether the protocol deviation was determined to be major or minor (grade).

12. CHANGES IN PLANNED ANALYSES FROM THE PROTOCOL

There have been no changes from the planned analyses in the protocol.

13. EFFICACY PARAMETERS

13.1 General Considerations

Unless otherwise specified, only data required per protocol (specified visits and retests per decision trees) will be displayed in summary tables. All data (including unscheduled visits, non-protocol mandated samples, etc.) will be displayed in listings.

For all device related endpoints, the results at each visit will be representative of the number of weeks the water device has been in use (i.e. visit 2 represents 8 weeks of use for that specific water device). Therefore, if a patient received a new water device midway through the study, the number of weeks in use would restart from 1.

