#### **4.4 Home Assessment and Installation**

During the Screening Period, all consented patients will have a home assessment to confirm the patient's home environment is suitable for the study. The patient's home environment must meet the AMIA APD Solution Generation System requirements to be eligible for enrollment (Refer to AMIA APD Solution Generation System Patient Guide for details of the system requirements). To provide schedule flexibility for the consented patient, Baxter Service or its designee may begin the home installation process during the Screening Period. System installation and product water from the WD (pre-sterilizing filters) testing are expected to take approximately two weeks. This will ensure the system is ready for activation after the patient completes his/her required in-center training on the AMIA APD Solution Generation System.

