### **8.7 Study Visits 2, 3 and 4 (Study Treatment Weeks 4, 8 and 12)**

Study Visits 2, 3 and 4 will occur during Study Treatment Weeks 4, 8 and 12 of the Study Treatment Period, respectively. In addition to the assessments included in Section 8.5, the following assessments will be completed during Study Visits 2, 3 and 4.

1. A simulated treatment will be set up by the patient. The dialysis solution generated during simulated treatment will be collected by the clinic nurse or designee from the system in the heater bag and used to evaluate the chemical composition of the final dialysis solution produced by patients using the AMIA APD Solution Generation System compared to the specifications of Baxter's approved Dianeal Low Calcium (2.5 mEq/L) PD Solution.
2. Product water from the WD (pre-sterilizing filters) will be also be collected by a clinic nurse or designee and tested to confirm that it conforms to ISO standard 13959 for microbiological (including endotoxin) and chemical contamination, and water from the holding bag (post-sterilizing filters), generated during a simulated treatment, will be collected and tested to confirm it does not exceed 0 CFU/mL for bacteria (no growth) and is < 0.03 EU/mL for endotoxins, consistent with Dianeal specifications for sterility. For more information regarding the differences in simulated treatment testing for product water from the WD and for product water from the holding bag, refer to points 2 and 3 in Section 8.6.
3. Assessment by an Investigator or a designee.

After the final Study Treatment Visit, patients are to transition back to treatments with AMIA with Baxter's approved Dianeal Low Calcium (2.5 mEq/L) PD Solution in their home environment and enter a 5-10 day Follow-up Period. Return of all investigational products and study related supplies will be scheduled during this time.

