13.2 Primary Efficacy Analysis

The primary efficacy endpoint of the study, chemical composition of the dialysis solution from the simulated treatment, will be analyzed descriptively using frequencies and percentages of those that meet specifications vs those that do not.

The dialysis solution will be considered as meeting specifications if all of the below parameters are within the specified limits:

Parameter	Limits
pH at 25°C	4.0 to 6.5
Color	≤ 15
5-HMF	≤ 0.25

Dextrose Hydrous Assay:	
1.5% Dextrose, Hydrous	1.40 to 1.60
2.5% Dextrose, Hydrous	2.38 to 2.62
4.25% Dextrose, Hydrous	4.00 to 4.50
Sodium Lactate (g/L)	4.23 to 4.73
Sodium (mEq/L)	125 to 139
Chloride (g/L)	5.28 to 5.83
MgCl ₂ 6H ₂ O (g/L)	0.041 to 0.061
CaCl ₂ 2H ₂ O (g/L)	0.157 to 0.210

If any one of the above parameters tested fall outside of the limits given, then the particular test is considered not meeting specifications. If any of the above parameters were not tested, then the particular test is considered missing. All testing for dialysis solution will be completed at the Baxter Round Lake laboratory facility.

The testing of the dialysis solution occurs four times throughout the trial: once at simulated treatment (week 1), and once at each of the treatment visits (weeks 4, 8, and 12). The Dextrose Hydrous % will be set to the following for each of the weeks: 1.5% at weeks 1 and 12, 2.5% at week 4, and 4.25% at week 8.

There will be three summaries of these data: one based on initial values, one based on retest values (as mandated per decision tree), and one based on the most recent test values. These three summaries will be done on a combination of all visits and individually for each of the visits.

In addition to the above, there will be two additional tables detailing the chemical composition of the dialysis solution. The first will show the test results (met vs did not meet specifications) for each of the individual parameters, and the second will be a descriptive summary (n, mean, standard deviation, minimum, median, and maximum) of the results of each of the individual parameters.

If a patient had been re-enrolled in the study, all data will be gathered and summarized for this analysis.

The test results will also be listed. Patient's age, sex, race, and weight at baseline will not be shown for this listing. This listing will include all enrolled patients.

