16.3 Visit Windows/Unscheduled Visits

The visit windows are defined below:

Table 1: Visit Windows

Time-point/Visit	Time Window
Screening	Approximately 3 weeks
Baseline period	Approximately 2 weeks after Screening
Simulated Treatment (Visit 1)	Up to 7 days prior to Day 1 of Study Treatment period
Visit 2	Any time during week 4 of treatment
Total Kt/V_{urea} visit	Any time between week 5 thru 8 of study treatment
Visit 3	Any time during week 8 of study treatment
Visit 4	Any time during week 12 of study treatment
End of Study Visit or Early Termination visit	5 days after last treatment with AMIA APD Solution Generation System

In the instance that multiple results are collected at the baseline visit, the last available result will be used in the analyses. For assessments collected post-baseline, the first available result will be used, or the assessment from the withdrawal visit will be used if the nominal visit result is unavailable. All re-tests will be presented in safety listings.

Results from unscheduled visits will not be included in the table summaries. These values will only be presented in the listings.

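### SAP 13.1 and 14.1.1 equate Visit 2 with 8 weeks of water-device use although Visit 2 is in week 4, and the linked restart rule also reaches dialysis-solution results, whose dextrose strength follows study week

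*SAP*

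**What the plan says.** **What a visit represents.** SAP 13.1 (efficacy) and 14.1.1 (primary safety) carry the same rule: for device-related endpoints, a visit's results stand for the time the water device has been in use. The illustration is that "visit 2 represents 8 weeks of use for that specific water device". The rule continues: "if a patient received a new water device midway through the study, the number of weeks in use would restart from 1".

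**Which endpoints.** The rule is worded for every device-related endpoint. In its text on re-enrolled patients, SAP 7.3 gives its examples as "device-related analyses (e.g. chemical composition testing of dialysis solution, microbiological testing of product water".

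**When the visits are.** SAP Table 1 gives the Visit 2 window as "Any time during week 4 of treatment". Protocol 8.7 says: "Study Visits 2, 3 and 4 will occur during Study Treatment Weeks 4, 8 and 12".

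**Dextrose strength and reporting.** SAP 13.2 sets the strength of the simulated treatment at "1.5% at weeks 1 and 12, 2.5% at week 4, and 4.25% at week 8". Of the initial, retest and most-recent summaries it says: "These three summaries will be done on a combination of all visits and individually for each of the visits". SAP 14.1.2 and 14.1.3 plan the same for product water and holding-bag water.

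**Installation.** Protocol 4.4 says: "System installation and product water from the WD (pre-sterilizing filters) testing are expected to take approximately two weeks". Installation may begin in Screening, so the device is in the home before the first treatment.

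**The concern.** The example gives a figure for Visit 2 that belongs to Visit 3. It sits inside the rule that tells the programmer what a visit means, and it appears in two sections.

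The restart rule also creates a second time index. For water endpoints, indexing by device age is sensible, because the question is how a given device performs as it ages. For dialysis solution, the strength produced depends on the study week and not on the age of the device. The two indexes agree only while the first device stays in place. After a replacement within the same enrolment, the SAP does not say which index defines a by-visit row, nor when a device starts to be in use. Two programmers could build different by-visit tables for the primary endpoints from the same text.

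**Working it through.** **Step 1: the stated figure.** From protocol 5.3 and 8.7, SAP Table 1 and SAP 13.2, Visits 1, 2, 3 and 4 correspond to weeks 1, 4, 8 and 12. Visit 2 is therefore week 4. The SAP's figure of 8 is not reproduced, and the only visit at week 8 is Visit 3.

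**Step 2: whether another clock gives 8.** The SAP does not say when use begins, so count from installation.
- Week 4 is days 22 to 28, which is 21/7 = 3.0 to 27/7 = 3.9 weeks after Day 1.
- Assume installation 2 to 5 weeks before Day 1: about two weeks from protocol 4.4 at the latest, and 3 + 2 weeks (Screening plus Baseline) at the earliest. Visit 2 then falls 3.0 + 2 = 5.0 to 3.9 + 5 = 8.9 weeks after installation.
- With a wider assumption of 0 to 5 weeks, the range is about 3 to 9 weeks.

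Eight weeks is possible for some patients but is not a fixed value for Visit 2. The permitted 14-day interruption cannot explain it, because it is allowed only after the Kt/V assessment in weeks 5 to 8. It can separate calendar weeks from treatment weeks only at later visits.

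**Step 3: the restart rule applied to dialysis solution.** Assume that by-visit results are indexed by device week. The SAP does not state this. For a replacement at the end of study week *r*, device week = study week − *r*. Row strengths are 1.5, 2.5, 4.25 and 1.5% at weeks 1, 4, 8 and 12.

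| Replaced at end of week | Later samples: study week (strength) → device week | Result |
|---|---|---|
| 3 | 4 (2.5%) → 1; 8 (4.25%) → 5; 12 (1.5%) → 9 | first falls in a 1.5% row; others in no row |
| 4 | 8 (4.25%) → 4; 12 (1.5%) → 8 | fall in the 2.5% and 4.25% rows |
| 6 | 8 (4.25%) → 2; 12 (1.5%) → 6 | no row |
| 7 | 8 (4.25%) → 1; 12 (1.5%) → 5 | first falls in a 1.5% row; other in no row |
| 8 | 12 (1.5%) → 4 | falls in the 2.5% row |
| 11 | 12 (1.5%) → 1 | strengths agree |

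For *r* = 1, 2, 5, 9 and 10, as for *r* = 6, every later sample falls on a device week with no row. Only *r* = 11 leaves sample and row at the same strength.

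**Step 4: size.** Assume 30 completers with four samples each: 30 × 4 = 120. One replacement at *r* = 4 moves 2 samples, and 2/120 = 1.7%. The week-4 row would hold 30 + 1 = 31 results, one of them from another strength. The week-8 row would hold 30 − 1 + 1 = 30, also with one from another strength. The week-12 row would hold 30 − 1 = 29.

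**Step 5: what is not touched.** SAP 13.2 gives separate dextrose limits for each strength (1.40 to 1.60, 2.38 to 2.62, 4.00 to 4.50). If each sample is judged against the limits for the strength it was made at, its pass/fail result and the all-visits count do not change.

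**The case against.** The strongest reply is that the 8 is only an illustration in parentheses. Visit timing is fixed consistently elsewhere, a programmer would take it from Table 1, and no limit or count uses the 8. On this view a wording correction is enough. It stands that no calculation uses the figure. But the illustration is the only explanation of an analysis rule, it is stated twice, and the schedule contradicts it.

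Second, the restart rule resets a count of weeks. It does not say that a sample moves to another visit row, and Table 1 defines visits by study-treatment week. This stands: a reader might infer that the SAP orders results to be re-filed by device week, and it does not. The SAP leaves the choice open.

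Third, a reader might infer that strengths would be blended in means and standard deviations. The documents do not support that. The by-visit breakdown is stated for the overall met/not-met summaries and not for the two individual-parameter tables, and all results are listed.

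Fourth, the case should be rare. Protocol 6.5.8.1 calls for product-water samples from each device at installation and bars home treatment until post-installation results are reviewed, and protocol 4.4 allows about two weeks for installation and testing. Missing more than 4 consecutive days, device issues included, is a ground for withdrawal (protocol 3.5.1). The same section foresees re-enrolment after a water-device replacement, and SAP 7.3 lists replacement as a discontinuation reason. A re-enrolled patient restarts with study week and device week aligned. This largely stands. Withdrawal is at the investigator's discretion, though, and the SAP itself provides for a new device midway through the study, so some cases may remain.

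**Conclusion.** The concern holds in two limited parts. First, the 8-week figure for Visit 2 is an error: by the plan's schedule it is week 4, and no clock makes 8 a fixed value. Second, as worded, the restart rule covers dialysis-solution composition, where device week and dextrose strength separate after a replacement within one enrolment.

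Only the by-visit met/not-met summaries are exposed. The size is 2 of 120 planned samples (1.7%) for one replacement at the end of week 4. That rests on 30 completers, four samples each, and indexing by device week. The documents give no number of replacements within one enrolment, and it is likely to be small.

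A reader might go further and conclude that the overall primary efficacy result is at risk. The documents do not support this, provided that each sample is judged against the limits for its own strength, which the SAP implies but does not state. Nor do they settle which clock is right. Counting cumulative treatment weeks would put the pre-treatment Visit 1 at week 0. Time since installation is defensible for water endpoints, because protocol 6.6 keeps the device powered and connected between treatments. The point is worth correcting because the remedy is cheap, not because the conclusions of this descriptive study are in doubt.

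**What to change.** - In SAP 13.1 and 14.1.1, change the example to 4 weeks of use at Visit 2.
- Limit the restart rule to product water and holding-bag water.
- Summarise dialysis solution by study visit and by dextrose strength produced, and state that the limits follow that strength.
- Name one start point for weeks in use. The choice is the sponsor's, with the pre-treatment Visit 1 labelled week 1. If the count runs from installation, say that the visit-to-week example is a nominal label.
- Say where water samples taken after a replacement are reported when their device week is not 1, 4, 8 or 12, for example in a separate row.

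The cost is SAP wording in two sections and one derived variable. No new data are needed: protocol 8.4 already records device details at installation and whenever the device changes.
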